Sensitivity #6	Restrict to patients with Exon19 deletion only (databases for which this information is available)	FLAURA only included patients with sensitizing mutation (Exon19 deletion) but this information is not consistently provided across databases which is why in primary analyses we include all patients with any EGFR mutation assuming that it is sensitizing given that these patients initiated osimertinib, gefitinib or erlotinib	Target population is genetically more identical and increases specificity of biomarker measurement	Information not consistently available
Sensitivity #7	Re-weighting of strong risk factors and/or treatment effect modifiers distribution to match that of FLAURA	In the presence of effect modification, treatment effect estimates may be different if	Re-weighting adjusts for differences in distributions of key risk factors and/or	Re-weighting risk factors/potential

		the distribution of strong risk factors/effect modifiers is different in the emulated cohort versus the trial cohort	treatment effect modifiers (see subgroup analysis in Table 7)	effect modifiers to match the FLAURA trial and simultaneously balancing them across treatment groups may be challenging due to differences in measurement
Sensitivity #8	Including patients who have had at least 1 visit 90 days prior to treatment initiation	EHR are often lacking data continuity, and this analysis uses the requirement of 1 visit as a proxy for continuous observation periods	Considers aspect of data continuity	There may be patients who are put on treatment immediately in which case they are falsely excluded
Sensitivity #9	Exclusion of patients with osimertinib exposure before April 18, 2018	There are a few patients who are observed to have received osimertinib before its official approval (potentially due to off-label use in 1L, compassionate use, etc.)	Limits chances of exposure misclassification	May exclude truly eligible patients
Sensitivity #10	Restriction of eligible calendar time period from 2015 to 2022	Descriptive analyses indicate that there was a rapid uptake of new initiators of osimertinib immediately after approval in 2018 and a sudden decrease of SoC TKIs. This means there is hardly any overlap of patients pre/post 2018 and calendar cannot be sufficiently balanced	This sensitivity aims to mitigate the potential effects by imbalance in calendar time	Calendar time will overall remain imbalanced
Sensitivity #11	Addition of EDB2 and EDB4	EDB2 and EDB4 are not considered in primary analyses for reasons given in section 6.1.1.	Increased sample size and potentially broader coverage of general US cancer population	See limitations listed in section 7.

Sensitivity #12	Missingness is handled by restricting to patients with complete observations on a subset of the most important confounders ("complete cases")	Instead of imputing data, this sensitivity analysis restricts the analysis cohort to patients with complete observations on key confounders	Data will not be imputed and missingness is assumed to be missing completely at random	The restriction to complete cases will significantly decrease sample size. To limit the attrition of patients with partially observed covariates, it won't be possible to use all covariates used in the main analysis propensity score model, but only consider key covariates with overall low proportions of missingness (age, sex, etc.)
-----------------	---	--	--	--

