Outcome:	Time to all-cause mortality (OS)		
Time (when follow up begins and ends):	From the day of treatment initiation until death or last observed clinical activity/last sign of the patient being alive or data cut-off, whichever occurred earlier		
Setting:	1L EGFRm+ metastatic NSCLC		
Main measure of effect:	Primary: Hazard ratio (95% CI) for overall survival		
	Secondary: median overall survival time (difference) in % (95% CI)		

The emulation of the main protocol elements of the FLAURA is illustrated side by side in **Table 2**.

Table 2. Trial emulation table summarizing the main protocol elements of the FLAURA trial and the planned emulation.

Protocol component	FLAURA RCT	Emulation	
Eligibility criteria	 - Age at least 18 years at time of randomization - Adenocarcinoma of the lung - Locally advanced or metastatic NSCLC, not amenable to curative surgery or radiotherapy - Tumour harbours one of the 2 common EGFR mutations known to be associated with EGFR-TKI sensitivity (Ex19del, L858R), either alone or in combination with other EGFR mutations - Patients must be treatment-naïve for locally advanced or metastatic NSCLC and eligible to receive first-line treatment with gefitinib or erlotinib 	there needs to be evidence of metastatic disease at time of treatment initiati (EDB4) - Evidence of any EGFR mutation in the 180 days before/on treatment initiati - Treatment needs to be first-line for advanced (EDB1) or metastatic (EDB2) disease or patients with prior exposure to any potential antineoplastic treatment	
Treatment	 World Health Organization Performance Status of 0 to 1 No prior treatment with any systemic anti-cancer therapy for locally advanced/metastatic NSCLC No prior treatment with an EGFR-TKI. osimertinib versus SoC EGFR-TKI (erlotinib or gefitinib) 	osimertinib versus SoC EGFR-TKI (erlotinib or gefitinib)	
strategies Assignment procedures	Random assignment to receive either osimertinib or SoC EGFR-TKI (gefitinib or erlotinib) in a 1:1 ratio	1:1 matching of patients based on their propensity to initiate osimertinib as opposed to SoC EGFR-TKI	
Follow-up period	Time from randomization until death from any cause or censoring of patients who did not die on the basis of the last recorded date that the patient was known to be alive	Time from treatment initiation until death from any cause or censoring of patients who did not die on the basis of the last recorded date that the patient was known to be alive	
Outcome	Overall survival	Overall survival	

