Causal contrast	Intent-to-treat effect	Counterfactual comparison of initiation of osimertinib as opposed to SoC EGFR-TKI	

6. Research methods

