6.6.5. Context and rationale for outcome(s) of interest

The primary outcome for the database study was defined to emulate the primary outcome for the trial, time from index to death due to any reason (overall survival). Operational definitions:

- EDB1: Time in {days, months and years} from index date to death due to any reason. The date of death is de-identified to month-level granularity or (rarely) to year-level granularity and the date of death is therefore imputed to the 15th of a month or mid-year/July 2 of the year of death, respectively. In If there is no indication that a patient died during the study period, the patient is censored. The censoring date is defined as the last visit or treatment encounter or data cut-off date, whichever occurred earlier. The overall survival endpoint is operationalized using a parameterized R function edb1_get_os() and more details can be found in the attached pdf documentation.
- EDB2: Time in {days, months and years} from index date to death due to any reason. If there is no indication that a patient died during the study period, the patient is censored. The censoring date is defined as the last observed activity date or data cut-off date, whichever occurred earlier. Activity dates are defined as documented in Table 4. Dates used to derive time to all-cause mortality may have some associated imprecision such that the date of death is either known completely, the year and month is known or only the year is known. The overall survival endpoint is operationalized using a parameterized R function edb2_get_os() and more details can be found in the attached pdf documentation.

Table 4. Relevant clinical activities considered to derive last activity date for censoring.

Table / clinical activity considered	Dates considered
Adverse events	Event date
Therapy (cellular, systemic, radiation, surgery)	Start and end dates or declined intervention date, surgery date, assessed resection dates
Palliative care referral	Referral date
Visits	Contact/visit date
Vitals	Assessed date
Labs	Lab date
Biomarkers	Specimen collection date
Patient observation period	Start and end dates
Demographics	Date of most recent contact with provider, date patient was diagnosed with a second primary malignancy
Performance assessments	Documented date, reported date

[figure not shown]
Secondary diagnoses	Diagnosis date
Progression, histology, lymphovascular invasion, metastatic sites, pancoast tumor, perineural invasion	Assessed date

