To estimate the treatment effects for osimertinib using propensity score matching across imputed datasets we will apply the "within" approach using the "MatchThem" R package. 28,29 That is, propensity score matching and the estimation of the treatment effect are performed in each imputed dataset separately and resulting treatment effect estimates are combined using Rubin's rule. In this study, this will be implemented by matching eligible patients on their propensity to initiate osimertinib using a 1:1 nearest neighbor matching algorithm without replacement and a caliper of 1% of the standard deviation of the propensity score. The resulting covariates balance will be assessed by computing and visualizing ASMDs before and after matching across datasets. As compared to a single dataset matching approach, this can lead to a range of ASMDs per covariate due to random variation across imputed datasets for which an example (using simulated data) is illustrated in Figure 5. If sufficient balance can be established, a Cox proportional hazards regression model will be fit to estimate the marginal average treatment effect in the matched population. Since in most databases there are more osimertinib patients than patients in the control arm, the estimand will rather correspond to the ATC than the ATT. Confidence intervals will be estimated using cluster-robust standard errors. 30 As a secondary endpoint, we will additionally estimate the median OS survival time difference between the two exposure groups using the Kaplan-Meier method. It should be noted that due to administrative and de-identification purposes, the date of death is often only available at the month- or year-granularity level, in which case the date of death will be imputed to the 15th of a month or July 2nd of a year, respectively (depending on the database). In rare cases, this can lead to negative/implausible follow-up times if the date of death is very close to the index date. These patients will be excluded from the analysis.

The final hazard ratio and median OS survival time difference estimates for each database will then be combined using Rubin's rule.^{27,31} To arrive at a single estimate across databases, the final estimates will be summarized through a meta-analytic fixed effects model.³² A summary of the analytic approach is summarized in Table 7 and an example workflow with simulated data and annotated code can be found https://example.com/here/beta-arrive

A. Primary analysis

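### The exclusion for negative or implausible follow-up (Protocol 6.7.1) removes, besides date errors, initiators who died shortly after time 0; the expected effect is small and the repair is cheap

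*Protocol*

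**What the plan says.** Section 6.7.1 explains that coarse death dates are completed by imputation and adds: "In rare cases, this can lead to negative/implausible follow-up times". The sentence continues, and the rule follows: "if the date of death is very close to the index date. These patients will be excluded from the analysis".

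For EDB1, the only database in the primary analysis, section 6.6.5 says that dates are coarsened to the month or, rarely, the year, and that "the date of death is therefore imputed to the 15th of a month or mid-year/July 2 of the year of death". Patients without a recorded death are handled differently: "The censoring date is defined as the last visit or treatment encounter or data cut-off date, whichever occurred earlier".

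Section 5, Table 2 defines emulated follow-up as "Time from treatment initiation until death from any cause or censoring of patients who did not die". It gives the causal contrast as "Counterfactual comparison of initiation of osimertinib as opposed to SoC EGFR-TKI", set beside the trial's intent-to-treat effect. Section 6.6.1 puts time 0 at drug initiation, and section 6.6.6 limits the study to intention-to-treat analyses. None of the twelve sensitivity analyses in Table 9 varies the exclusion (number 4 moves only the censoring date of patients without a death), and section 7 does not list it as a limitation.

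**The concern.** Imputation can create a negative time only for a patient with a recorded death, because everyone else is censored at a real encounter date or at data cut-off. Take two eligible patients who both start on the 20th. One dies on the 28th of that month, has death set to the 15th, and is removed. The other survives the month and stays. Whether a patient belongs to the cohort then depends on what happened after time 0.

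At stake are true events of the primary endpoint in an analysis that is otherwise organised around initiation and intention to treat. If early deaths were common and unevenly spread between the arms, the hazard ratio would move. No planned analysis would show it.

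**Working it through.** **Step 1. Separate the two kinds of record that the rule removes.**

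| Recorded death period against index period | Source of the negative time | Compatible with death after time 0? |
|---|---|---|
| Earlier month (or year) | The recorded date itself | No; a date error |
| Same month (or year) | The imputation only | Yes |

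The concern is with the second row.

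**Step 2. How late can a removed death be?**
- Month level: index on the 16th, death on the 31st, imputed to the 15th. True survival is 15 days.
- Year level: index July 3, death December 31, imputed to July 2. True survival is 181 days. This is the single extreme, and section 6.6.5 calls year-level dates rare.

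**Step 3. Share of patients removed, month-level dates.** The protocol gives no figure beyond calling such cases rare, so there is nothing to reproduce.

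Inputs from section 4: median survival 31.8 months (comparator) and 38.6 months (osimertinib). Assumptions: exponential survival, index dates spread evenly over a 365-day year, 30.4375 days per month.

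Daily hazard λ = ln 2 / (median × 30.4375):
- comparator: 0.6931 / 967.9 = 0.000716
- osimertinib: 0.6931 / 1174.9 = 0.000590

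Share = average over the 365 index days of [day of month > 15] × (1 − exp(−λ × (days to month end + 0.5))).

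There are 185 index days after the 15th, with 1,430.5 days at risk in total, or 1,430.5 / 365 = 3.92 days per patient on average. To first order the share is 3.92 × λ, that is 0.28% and 0.23%. The exact sums are:

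| | Comparator | Osimertinib |
|---|---|---|
| Negative follow-up only | 0.280% | 0.231% |
| Zero-day follow-up (index on the 15th) also removed | 0.317% | 0.261% |

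This is between two and a little over three patients per 1,000 in each arm. Had every death date been year-level, the same sum over index dates after July 2 would give 3.1% and 2.6%. That applies only to the rare year-level records.

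**Step 4. Effect on the hazard ratio.** Simulated Cox fits used 1,000,000 patients per arm, true hazard ratio 0.8, and uniform censoring at 12 to 72 months (assumed). Early deaths were either kept at 0.5 day or excluded.

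| Scenario (all multipliers and the 5% year-level share are assumptions) | Kept | Excluded |
|---|---|---|
| Constant hazards, month-level dates | 0.7995 | 0.7994 |
| Hazard ×3 in both arms for 90 days, 5% year-level dates | 0.8005 | 0.8005 |
| Hazard ×5 comparator, ×2 osimertinib for 90 days, month-level dates | 0.6139 | 0.6196 |
| Same, 5% year-level dates | 0.6143 | 0.6214 |
| Reversed (×2, ×5), 5% year-level dates | 1.0387 | 1.0263 |

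With proportional early hazards the shift is 0.0002 or less. It reaches about 0.006 to 0.012 only when early hazards are made sharply unequal.

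**The case against.** The strongest reply is that this does not matter. The protocol already describes the cases as rare, and under its own medians the hazard ratio does not move. The scenarios that produce a visible shift also move the underlying hazard ratio to about 0.61 or 1.04, so the exclusion would be a minor part of the picture. This stands, and it sets the severity. It does not make an outcome-dependent exclusion correct.

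Four further points stand in whole or in part.

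- **Power.** A reader might infer that losing events takes the study below its stated 80%. The documents do not support this. Section 10.3 computes power from the average number of observed events in the imputed and matched datasets. If the exclusion came first, the 80% already reflects it. The event count is not readable. By Schoenfeld's formula, 80% corresponds to (1.960 + 0.842)² / (0.25 × (ln 0.8)²) ≈ 631 events, but this does not show whether the exclusion came before the count.
- **Zero-day follow-up.** A reader might infer that its handling was left open. Section 6.6.5 refers to separate documentation of the survival function, which is not at hand and may settle it.
- **The 181-day case.** It is a corner case and should not be read as typical. It shows only that the protocol's description of these deaths as very close to index does not fit year-level dates.
- **Date errors.** Some removed records will be genuine errors. Excluding those is reasonable.

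**Conclusion.** The point holds as a minor flaw in a rule that the protocol states outright. For same-month and same-year deaths the rule discards records compatible with a real event after time 0, and it does so because of the outcome. That conflicts with the follow-up definition and causal contrast in Table 2 and with the intention-to-treat statement in section 6.6.6.

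The size rests on exponential survival at the trial medians, evenly spread index dates and mainly month-level death dates. Real early mortality in EDB1 and its share of year-level dates are not in the readable text. The effect would be larger if early deaths were frequent and clearly different between arms, or if year-level dates were common. Material bias in the hazard ratio is a reading that the documents do not support. The case for changing the rule is consistency with the protocol's own design at almost no cost.

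**What to change.** Amend the exclusion sentence in section 6.7.1 as follows.

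1. If the imputed death date falls on or before the index date, but the recorded death month (or year) is the same as that of the index date, keep the patient as an event.
2. Take the later of the index date and the last documented encounter in that period. Set the death date to the midpoint between that date and the end of the month (or year), with at least 1 day of follow-up. Using the last encounter avoids placing a death before a visit on record.
3. Leave all other imputed dates unchanged.
4. Exclude only when the recorded death month or year precedes that of the index date.
5. Report the numbers kept and excluded, by arm.

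The cost is a short text change and a small change to the survival derivation function. There are two downsides. The kept times are approximate, off by at most about 8 days for month-level dates (half of the 16 days from the 15th to the 31st) and about 91 days for year-level dates (half of the 182 days from July 2 to December 31). A few same-period date errors that cannot be detected may also be counted as events.

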The purpose of this protocol is to describe the emulation of the **FLAURA trial**.^{5,6} FLAURA was a Phase III, double-blind, randomised study assessing the efficacy and safety of AZD9291 (= osimertinib, 80 mg orally, once daily) versus a standard of care (SoC) Epidermal Growth Factor Receptor (EGFR) Tyrosine Kinase Inhibitor (TKI) (either gefitinib [250 mg orally, once daily] or erlotinib [150 mg orally, once daily]) in patients with locally advanced or metastatic EGFR sensitizing mutation (EGFRm+) Non-small Cell Lung Cancer (NSCLC) who are treatment-naïve and eligible for first-line treatment with an EGFR-TKI.

The primary trial estimate targeted for emulation is a hazard ratio (HR) for death (overall survival) of 0.80 (95% CI 0.64 to 1.00) with a median overall survival time of 38.6 months (95% CI 34.5 to 41.8) in the osimertinib group and 31.8 months (95% CI, 26.6 to 36.0) in the comparator group. Market availability of osimertinib began April 18, 2018 based on the progression-free survival (PFS) endpoint.

The PFS endpoint was published in the NEJM on November 18, 2017 (PMID 29151359).5

The OS endpoint was published in the NEJM on November 21, 2019 (PMID 31751012).6

5. Research question and objectives

The primary and secondary research question is summarized in Table 1.

A. Primary research question and objective

Table 1. Primary and secondary research questions and objective.

Objective:	To compare the overall survival [OS] in patients who initiated osimertinib versus patients who initiated erlotinib or gefitinib.			
Hypothesis:	Initiation of osimertinib improves overall survival time as compared to initiation of erlotinib or gefitinib			
Population (mention key inclusion-exclusion criteria):	 Age at least 18 years Locally advanced or metastatic Non-small Cell Lung Cancer (NSCLC) patients who receive treatment without curative intent The line of therapy for patients in EDB1 and EDB2 is implicitly advanced/metastatic because the line of therapy classification starts after their advanced/metastatic diagnosis in the respective database In EDB4, patients must explicitly have any evidence of a metastasis prior initiating Osimertinib, gefitinib or erlotinib. 			

	Adenocarcinoma histology		
	EGFR sensitizing mutation (any EGFRm+)		
	Treatment-naïve and eligible for first-line (1L) treatment with an EGFR-targeted tyrosine kinase inhibitor (TKI)		
	• ECOG 0 or 1		
Exposure:	Initiation of osimertinib		
Comparator:	Initiation of erlotinib or gefitinib		

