- Rationale for excluding of EDB4 from primary analysis: As shown in Table 3, the patient identification period in EDB4 starts on 10/01/2018 which is after the official approval of osimertinib for 1L metastatic EGFRm+ NSCLC. This means there are limited "control" patients captured in EDB4 from the pre-osimertinib era (see Figure 15). Given the documented clinical benefit and the corresponding rapid uptake of osimertinib after April 2018, it could be assumed that patients who initiated the "old" standard-of-care after April 2018 did so for specific reasons. This means these patients may be likely to be significantly different in their baseline characteristics and prognosis for reasons that may not be measurable.

For these reasons, only EDB1 will be used for the main analysis. However, EDB2 and EDB4 will be considered as part of a sensitivity analysis in which all databases are individually analyzed and treatment effect estimates are pooled using a meta-analytic fixed effects model (see sensitivity analysis #11 in Table 9).

Data source provenance/curation: In brief, all databases provide EHR-derived oncology-specific patient-level information which are either derived directly (e.g., through structured data fields and dropdown menu selections) from EHR and/or undergo semi-automated abstraction processes from unstructured reports. The detailed data provenance, abstraction processes and implemented business rules to curate and prioritize certain variables may vary by database and can be found in legacy publications by the data partners.

Table 3. Metadata about data sources and software.

ie 5. Metadata about data soui	EDB1	EDB2	EDB4
Data Source(s):	EHR-derived	EHR-derived	EHR-derived
Study Period:	Patient identification period: 01/01/2011-04/30/2024 with follow-up information through data cut-off date on 04/30/2024	Follow-up information through 02/24/2023 (there is no specific time period restrictions for patient eligibility)	Patient identification period: 10/01/2018-09/30/2023 with follow-up information through data cut-off date on 09/30/2023.
Eligible Cohort Entry Period:	Anytime at start of study drug initiation	Anytime at start of study drug initiation	Anytime at start of study drug initiation
Data Version (or date of last update):	Delivery: Jul 11, 2024	Delivery: Sep 8, 2023 Updated (LoT addition): Mar 11, 2024	Delivery: Oct 24, 2023 Updated (demographics): Feb 29, 2024

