Table 7. Primary and subgroup analysis specification

able 7. Primary and Subgroup	7 dilarysis specification
Hypothesis:	Initiation of osimertinib decreases the hazard of all-cause mortality as compared to initiation of erlotinib or gefitinib
Exposure contrast:	Initiation of osimertinib vs. initiation of erlotinib or gefitinib
Outcome:	Time to all-cause mortality (overall survival)
Databases used:	EDB1
Analytic software:	R 4.3.2. Version control of code and R packages will be established through git and Posit package manager, respectively. All packages are frozen to their most recent version as of April 24, 2024.
Model(s): (provide details or code)	See example code https://drugepi.gitlab-pages.partners.org/encore/flaura-nct-02296125/ (access only through MGB network for authorized personnel)
Confounding adjustment method	Name method and provide relevant details, e.g. bivariate, multivariable, propensity score matching (specify matching algorithm ratio and caliper), propensity score weighting (specify weight formula, trimming, truncation), propensity score stratification (specify strata definition), other. 1:1 propensity score nearest neighbor matching without replacement and a caliper of 1% of propensity score standard
Ministration of the	deviation
Missing data methods	Name method and provide relevant details, e.g. missing indicators, complete case, last value carried forward, multiple imputation (specify model/variables), other.
	Multiple imputation by chained equations using a random forest imputation model across all covariate types. The number of imputed datasets will be determined by the average proportion of missing values across all partially observed covariates. Imputation models will include all variables of the substantiative model, i.e., exposure, outcome, confounders/prognostic factors and additional auxiliary covariates.
Subgroup Analyses	List all subgroups
	In subgroup analysis, multiple imputation, propensity score matching and balance assessment will be conducted within each subgroup separately. The treatment effect will be estimated in the combined dataset by fitting a Cox proportional-hazards model that will include the exposure, the subgroup covariate of interest, and the treatment-by-subgroup interaction term. 1. Sex (Male, Female)
	2. Age (<65, ≥65)* 3. Resp (athricity (Agian Non Agian)*
	3. Race/ethnicity (Asian, Non-Asian)*4. Smoking history (current/former, never)5. ECOG (0, 1)*

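### Table 7 matches within each subgroup level but fits one Cox model with a shared baseline hazard; with unequal follow-up by arm, a subgroup effect that changes over time would bias the interaction

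*Protocol*

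**What the plan says.** The Subgroup Analyses row of Table 7 (Protocol, Section 6.7.1) states that "multiple imputation, propensity score matching and balance assessment will be conducted within each subgroup separately". The treatment effect is then estimated in the combined data by "fitting a Cox proportional-hazards model that will include the exposure, the subgroup covariate of interest, and the treatment-by-subgroup interaction term". The row mentions neither stratification of the baseline hazard nor a check of proportionality between subgroup levels. The subgroups are sex, age, race/ethnicity, smoking history and ECOG. Age, race and ECOG are flagged as having shown significant differences in FLAURA.

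Three other places fix how long each arm can be observed:
- Section 6.1.1, Table 3, for EDB1: "Patient identification period: 01/01/2011-04/30/2024 with follow-up information through data cut-off date on 04/30/2024".
- Section 4: "Market availability of osimertinib began April 18, 2018".
- Table 9, sensitivity #10: "there is hardly any overlap of patients pre/post 2018 and calendar cannot be sufficiently balanced".

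Section 7 adds that calendar year determines treatment completely and cannot be balanced.

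**The concern.** Matching within levels yields a self-contained comparison for each level. The combined model does not keep those comparisons separate. It pools the risk sets and ties the levels together through one baseline hazard and one constant subgroup HR.

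That matters here because the arms are observed over different spans. The subgroup main effect is learned from the SoC arm over long follow-up. The osimertinib arm contributes mainly early follow-up. If ECOG or age, for example, predicts death more strongly early than late, its average effect is larger in the osimertinib arm even when treatment works equally well in both levels. The model can express that difference only as an interaction.

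At stake are the subgroup HRs and interaction tests. Readers will set these beside FLAURA's subgroup results, and sensitivity #7 points to the same table for its effect modifiers.

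**Working it through.** **Potential follow-up in EDB1 (Table 3, Section 4)**
- Earliest SoC start, January 2011, to cut-off on 30 April 2024: 13 years 4 months, or 160 months.
- SoC start in April 2018 to cut-off: about 72 months.
- On-label osimertinib, from 18 April 2018: 0 to about 72 months.

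These are upper limits. Section 6.6.5 censors at the last visit or treatment encounter if that is earlier, and realised follow-up by arm is not given.

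**Models compared** (z = osimertinib, x = subgroup level)
- Planned: h(t) = h0(t)·exp(βz + γx + δzx).
- Stratified: h(t) = h0x(t)·exp(βz + δzx), with a separate baseline for each x. Its partial likelihood splits by level, so each subgroup HR is exactly that of its own matched cohort.

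**Size used.** The only design figure in the protocol is 80% power at HR 0.8, two-sided 5% (Section 10.3). Schoenfeld for 1:1 arms gives 4(1.960 + 0.842)²/(ln 0.8)² ≈ 631 events. The observed event count cannot be read from the text, so the 80% is consistent with 631 events but not independently confirmed.

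**Simulation A.** True HR 0.80 in both levels (true interaction ratio 1.00). SoC median is 31.8 months in the reference level (FLAURA comparator, Section 4). Follow-up is uniform over 72–160 months (SoC) and 0–72 months (osimertinib). About 631 events, 3,000 replicates.

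| Assumed subgroup effect on death | Planned: ratio, rejection | Stratified: ratio, rejection |
|---|---|---|
| HR 1.5 for 12 months, then 1 | 1.07, 6.6% | 1.00, 4.7% |
| HR 2 for 12 months, then 1 | 1.12, 10.2% | 1.00, 5.3% |
| HR 2 for 24 months, then 1 | 1.14, 11.9% | 1.00, 4.6% |
| HR 3 for 12 months, then 1 | 1.19, 16.7% | 1.00, 4.8% |
| HR 2 for 12 months, then 1; 1% per month loss | 1.10, 9.9% | 1.01, 5.6% |
| HR 3 for 12 months, then 1; 1% per month loss | 1.14, 12.9% | 1.00, 5.1% |
| HR 2 for 24 months, then 1; sensitivity #10 window | 1.11, 9.3% | 1.00, 4.8% |
| HR 1 for 24 months, then 2 (growing) | 0.89, 10.8% | 1.00, 5.3% |
| Control: HR 2 throughout | 0.99, 4.9% | 0.99, 4.9% |
| Control: equal follow-up, HR 2 for 24 months, then 1 | 0.99, 4.8% | 1.01, 4.9% |

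In the second row the planned model gives subgroup HRs of 0.75 and 0.84 (0.84/0.75 = 1.12). In other large-sample runs with equal follow-up and fading, the ratio stayed between 0.97 and 1.00.

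**Partial fading.** HR 2 falling to 1.5 at 12 months gives 1.02–1.05 in large samples. Simulation B used 700 patients per arm, 8% per year loss, SoC starts 2011–2018.3, osimertinib starts 2018.3–2024.3 and 300 runs:
- HR 2.0 falling to 1.2 at one year: ratio 1.063, rejection 8.0%.
- HR 1.6 falling to 1.3: ratio 1.036, rejection 5.3%.
- HR 1.5 falling to 1.2: ratio 1.035, rejection 6.0%.

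**Check by hand.** Rejection should be close to Φ(−1.96 + b) + Φ(−1.96 − b), with b = ln(ratio)/SE.
- HR 2 then 1 at 12 months: b = ln(1.119)/0.171 = 0.66, giving 10.1% (simulated 10.2%).
- HR 1.6 then 1.3: b = ln(1.036)/0.144 = 0.25, giving about 5.7% (simulated 5.3%).

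**Scaling.** For a change at 12 months without extra loss, ln(ratio) is close to 0.16 × ln(early HR/late HR): 0.064/0.405 = 0.16, 0.112/0.693 = 0.16 and 0.170/1.099 = 0.15 for the three 12-month rows. For 2 falling to 1.5 this predicts exp(0.16 × 0.288) = 1.05, the top of the simulated range.

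**Precision cost.** In simulation A the SD of the interaction estimate rises from 0.167 to 0.171 with a constant effect (2.4%). Elsewhere the rise is mostly 2–3%, and 4.7% at most (0.171 to 0.179).

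**The case against.** The strongest reply is that the decisive ingredient is not in the documents. The protocol calls its covariates prognostic but gives no time course for any of them, and with a constant subgroup effect the two models agree. That stands, and it makes the size a range over assumptions. The larger figures need a strong effect to disappear completely. Under moderate fading the bias is about a quarter of a standard error and rejection is close to nominal.

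It also stands that only subgroup results are touched. The protocol attaches no power claim or decision rule to them. Only a binary, ECOG-like factor was simulated, so nothing is shown for sex or race in particular.

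A further reply is that such a model is conventional, that proportionality checks are often left to the SAP, and that the linked code is not visible. This limits what can be said about safeguards. It does not change the point, because Table 7 itself names the model terms.

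Sensitivity #10 helps only in part. Restricting to 2015–2022 lowers the ratio from 1.14 to 1.11 in the 24-month scenario. Table 9 concedes that calendar time stays imbalanced, and it does not say that the restriction is repeated by subgroup.

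A reader might infer that the plan will produce false effect modification, or that the direction of bias is known. Neither is supported: an effect that grows with time reverses the sign (0.89).

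**Conclusion.** The point holds as a conditional weakness of the subgroup analysis. The shared-baseline assumption and the unequal potential follow-up both follow from the protocol; the time-varying subgroup effect is assumed. With a true HR of 0.80 in both levels, the false interaction ratio is about 1.02 to 1.06 for partial fading, with rejection of about 5 to 9% at a nominal 5%. It is about 1.1 to 1.2, with rejection of about 10 to 17%, only when a strong effect vanishes entirely. It is essentially absent with a constant effect or equal follow-up. Pair-clustered robust SEs would not remove it, since the fault is in the estimate and not in its variance.

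A reader might extend this to the main result. The documents do not support that: the primary model contains no subgroup term, and the median survival analysis in Table 8 has no subgroups. This is a worthwhile improvement, not a threat to the study's main conclusion.

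**What to change.** In the Subgroup Analyses row of Table 7, replace the subgroup main effect with stratification. Fit a Cox model with exposure and the exposure-by-subgroup interaction, stratified on the subgroup variable, with robust SEs clustered on matched pair and pooling by Rubin's rule. Fitting each level separately and comparing the two log HRs is equivalent.

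The cost is one sentence and one line of code, plus an interaction SE about 2 to 3% larger. That loss buys nothing if hazards between levels really are proportional. Otherwise it removes the bias: in simulation A rejection returned to 4.6–5.6%.
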